6.3 Dose modifications

6.3.1 Dose modification and dose delay

If a patient experiences a DLT, then treatment with LEE011 must be interrupted. For all toxicity grades, if the toxicity resolves to grade 1 or baseline within 1 week of onset, treatment may be resumed at the same or a lower dose level at the investigator's discretion and following discussion with Novartis. For toxicities that result in treatment delays of more than 7 but not more than 21 days, treatment may be resumed at a lower dose level. If a patient requires a dose interruption of > 21 days from the intended day of the next scheduled dose, then the patient must be discontinued from the study. In this event, more frequent follow up as outlined in cycle 1 to monitor this toxicity may be appropriate. Changes to the dose or schedule must be recorded on the Dosage Administration Record eCRF. All patients will be followed for AEs and for SAEs for 30 days following the last dose of LEE011.

Patients who have dose-limiting neutropenia with no other dose-limiting toxicity may receive the same dose in the next cycle with myeloid growth factor support or receive study drug at the next lower dose level. If dose-limiting neutropenia recurs after myeloid growth factor support is added, then the patient should be given the next lowest dose level for subsequent cycles and myeloid growth factor support should be administered.

Patients with extensive involvement of bone marrow who are not evaluable for hematologic toxicity but who have dose-limiting neutropenia should receive the same dose in the next cycle with myeloid growth factor support or receive study drug at the next lower dose level. Since these patients are permitted to have platelet transfusions to meet platelet criteria, no dose modifications will be made for dose-limiting thrombocytopenia.

If a patient experiences an adverse event that is considered to be related to LEE011 that requires interruption of treatment with LEE011, the following must be met in order to resume treatment with LEE011 (except for patients with bone marrow disease):

- ANC must be $\geq 1,000$ / μ l
- Platelet count must be $\geq 75,000$ / μ l
- All non-hematologic toxicities must be \leq grade 1 or returned to baseline
- Absence of any other DLTs, as described in [Table 6-2](#).

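### In Protocol 6.3.1 the marrow-disease exception sits on the lead-in to the restart list, so as written it also waives the non-hematologic restart conditions

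*Protocol*

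**What the plan says.** Protocol 6.3.1 handles interruption and restart in three steps.

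- **General rules, first paragraph.** "If a patient experiences a DLT, then treatment with LEE011 must be interrupted". For toxicity of any grade, "if the toxicity resolves to grade 1 or baseline within 1 week of onset", the patient may restart at the same or a lower dose, at the investigator's discretion and after discussion with the sponsor. The next tier covers toxicities that lead to "treatment delays of more than 7 but not more than 21 days, treatment may be resumed at a lower dose level". An interruption longer than 21 days ends participation.
- **Marrow paragraph, just before the list.** It concerns "Patients with extensive involvement of bone marrow who are not evaluable for hematologic toxicity". For dose-limiting neutropenia it offers the same dose with growth factor or the next lower dose. For platelets it reasons "Since these patients are permitted to have platelet transfusions to meet platelet criteria", and so makes no dose change for dose-limiting thrombocytopenia.
- **Restart list.** When a drug-related adverse event has forced an interruption, "the following must be met in order to resume treatment with LEE011 (except for patients with bone marrow disease"). Four bullets follow: ANC of at least 1,000/µl; platelets of at least 75,000/µl; a third that opens "All non-hematologic toxicities must be" and asks for grade 1 or lower, or baseline; and a fourth that reads "Absence of any other DLTs, as described in" Table 6-2.

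No bullet is restored for patients with marrow disease.

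**The concern.** Marrow infiltration can lower counts whatever the drug does, so relief from the ANC and platelet conditions makes sense. It does not explain a raised ALT, a long QTc or persistent grade 3 diarrhea. As placed, the bracket releases these patients from those conditions too.

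Two of the three major potential toxicities named in Protocol 1.2.1.1.3, hepatic toxicity and QT prolongation, fall in the part waived without a marrow reason. The patients are children and young people from 12 months of age.

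Take a marrow-positive child with a drug-related grade 3 ALT rise still unresolved on day 10 of a delay. Read literally, no explicit threshold in 6.3.1 blocks a restart at a lower dose. A marrow-negative child with the same event must first return to grade 1 or baseline. A site that restarted the first child would be following the text, so the restart need not appear as a protocol deviation.

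**Working it through.** The plan states no figure on this point, so the check is a reading of scope supported by simple counts.

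**Step 1. What the bracket lifts (6.3.1).**

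| Restart bullet | Lifted as written | Purely a blood count |
|---|---|---|
| 1. ANC | yes | yes |
| 2. Platelets | yes | yes |
| 3. Non-hematologic recovery | yes | no |
| 4. No other DLT in Table 6-2 | yes | no, mixed |

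Lifted: 4 of 4. Purely count-based: 2 of 4.

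**Step 2. What bullet 4 contains (Table 6-2).** Hematology 3, QT interval 1, gastro-intestinal 2, hepato-biliary 2, other non-hematologic 1. Total: 3 + 1 + 2 + 2 + 1 = 9. Non-hematologic: 9 − 3 = 6 of 9. These count criteria and do not measure risk.

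**Step 3. How the protocol limits marrow relief elsewhere.**

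| Place | Patients covered | What is relaxed |
|---|---|---|
| 5.2, inclusion criterion 5 (expansion part) | marrow metastases, standard counts not met | entry counts; evaluability for hematologic toxicity and hematologic DLT |
| 6.3.1, paragraph before the list | not evaluable for hematologic toxicity | handling of neutropenia and thrombocytopenia |
| 6.4.1 | not evaluable for hematologic toxicity | limits on transfusion and growth factor in Cycle 1 |
| 6.3.1, restart list | all with bone marrow disease | all four bullets |

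The first three rows are hematologic only. The last row alone goes further, so a narrower intent is likely, although that is an inference.

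**Step 4. What still protects these patients.**

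| Length of delay | Explicit recovery grade outside the list | Other rule |
|---|---|---|
| Toxicity resolved within 1 week | grade 1 or baseline, for everyone | sponsor discussion |
| 8 to 21 days | none stated | lower dose level |
| More than 21 days | not applicable | off study |

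The middle row spans 21 − 8 + 1 = 14 possible delay lengths in days. For those the list is the only explicit recovery threshold, and the bracket removes it. The requirement that no other DLT be present appears nowhere else in 6.3.1.

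**The case against.** The strongest reply is that the first paragraph of 6.3.1 is one sequence ordered by time to recovery: within a week, 8 to 21 days, longer. On that reading the grade 1 or baseline standard carries through, and the middle tier only adds a lower dose. An investigator would have to ignore the sense of the paragraph to restart during ongoing grade 3 toxicity. This has force and narrows the practical risk. It does not remove the problem, because the middle tier states no recovery grade and the list that would supply one is waived.

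Three stronger readings might be inferred, and the documents do not support them.

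- *That the DLT interruption rule lapses after Cycle 1.* Section 6.2.3 does define a DLT within the first 28 days. But 6.3.1 itself manages dose-limiting neutropenia that recurs, with consequences for later cycles, and 10.4.4 speaks of DLT data from later cycles. In dose modification the term may well mean a Table 6-2 event in any cycle. The strict 28-day reading would also empty bullet 4 for later events, so one cannot claim both that interruption lapses and that bullet 4 is a loss in those cycles.
- *That neutropenia with fever is a seventh criterion waived without reason.* Table 6-2 lists it under hematology, and criterion 5 makes its patients not evaluable for hematologic DLT. Requiring it to resolve in everyone may be sensible, but that is a clinical judgement.
- *That the count relief is itself wrong, or needs a floor.* Disease may lower counts later, even in a patient who met the standard entry counts. The criterion 5 values are entry criteria and are nowhere used for restart. As floors, they could hold a patient for platelets alone, which sits badly with the rule against dose changes for dose-limiting thrombocytopenia.

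**Conclusion.** The exception is wider than its rationale. As written it waives 4 of 4 restart conditions; bullet 3 in full and 6 of the 9 criteria behind bullet 4 have no marrow reason. The gap that matters is mainly delays of 8 to 21 days, together with the loss of the no-other-DLT condition.

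This rests on the literal position of the bracket and on reading the middle tier as it stands. The documents give neither the number of marrow-positive patients nor the number of restarts affected, so no headcount can be stated. Reach is limited: criterion 5 patients belong to the expansion part, and SAP section 4 reports halted enrollment with analyses of dose escalation only. The bracket itself names all patients with bone marrow disease, so it also covers marrow-positive escalation patients who met the standard counts.

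A reader might infer that dose finding is compromised. It is not: Cycle 1 DLTs are counted when they occur, and SAP 2.5 says the MTD/RDE was determined before enrollment was halted. This is a defect in re-exposure safety wording.

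**What to change.** Delete the bracket from the lead-in and attach it where the reason applies:

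1. ANC of at least 1,000/µl, except in patients with bone marrow disease.
2. Platelets of at least 75,000/µl, with the same exception.
3. Non-hematologic toxicity at grade 1 or lower, or back to baseline, in all patients.
4. No other Table 6-2 DLT; in patients with bone marrow disease, hematologic DLTs are not counted here, while non-hematologic DLTs count for everyone.

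Add no new count floors. Two choices belong to the sponsor and should be written down: whether count relief covers every marrow-positive patient or only those not evaluable for hematologic toxicity, and whether neutropenia with fever must have resolved in all patients.

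The cost is a protocol wording amendment with its usual approvals, and no extra assessments. Some restarts in marrow-positive patients may come later, and a few could reach the 21-day cap while waiting to recover. With enrollment halted, only patients still on treatment are affected.

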6.4 Concomitant medications

Refer to preclinical toxicity and/or clinical data found in the Investigator's Brochure.

6.4.1 Permitted concomitant therapy

Medications required to treat AEs, manage cancer symptoms, concurrent stable diseases and supportive care agents, such as packed red blood cells (PRBC)s, pain medications, anti-emetics and anti-diarrheals are allowed. Stable doses of steroids from study entry and oral contraceptive pills are permitted. The use of any other potential new concomitant medications may be discussed between the investigator and the sponsor on a case by case basis.

Transfusions or growth factor support for white cell counts, platelets or red blood cells are not permitted during Cycle 1, unless the patient has already experienced a DLT. Transfusions and growth factor support should not be used prophylactically during Cycle 1. Patients with bone marrow metastatic disease who are not evaluable for hematological toxicities are exempt.

The patient and/or patient's parent or guardian must be told to notify the investigational site about any new medications he/she takes after the start of the study drug. All medications (other than study drug) and significant non-drug therapies (including physical therapy and blood transfusions) administered during the study must be listed on the Concomitant Medications or Significant Non-Drug Therapies eCRF, respectively.

6.4.1.1 Corticosteroids

[figure not shown]
Chronic dosing of corticosteroids such as dexamethasone and prednisone is known to lead to induction of CYP3A enzymes, thereby potentially increasing the risk of reducing ribociclib drug exposure to subtherapeutic levels. Systemic corticosteroid treatment should not be given during the study, except for:

- Topical applications (e.g., rash), inhaled sprays (e.g., obstructive airways diseases), eye drops or local injections (e.g., intra-articular);
- A short duration (< 5 days) of systemic corticosteroids \leq to the anti-inflammatory potency of 4 mg dexamethasone (e.g. for chronic obstructive pulmonary disease, or as an antiemetic)

6.4.2 Concomitant therapy requiring caution

The following therapies are permitted in this study, however they should be used with caution:

- Medications that are moderate inhibitors or inducers of CYP3A4/5. (Refer to [Appendix 6](#)).

- Sensitive substrates of CYP3A4/5 that do not have a narrow therapeutic index (Refer to [Appendix 6](#)).
- Known BSEP inhibitors listed in [Appendix 6](#).
- Agents that are metabolized predominantly by CYP1A2 with a narrow therapeutic index and agents that are strong inhibitors of CYP1A2 listed in [Appendix 6](#).
- Medications that carry a moderate-low risk for QT prolongation listed in [Appendix 6](#).

Patients receiving such medications must be carefully monitored for potentiation of toxicity due to any individual concomitant medication, and may require dose titration of the drug substance.

6.4.3 Prohibited concomitant therapy

The following therapies are prohibited:

- Strong inducers or inhibitors of CYP3A4/5. In particular EIAEDs. (Refer to [Appendix 6](#)).
- Substrates of CYP3A4/5 with narrow therapeutic windows (Refer to [Appendix 6](#))
- Medications that carry a strong risk for QT prolongation (Refer to [Appendix 6](#))
- Concurrent anti-neoplastic therapy, including radiotherapy
- Patients should be instructed not to take grapefruit products/juice, or Seville (sour) oranges/juice while receiving LEE011 treatment throughout the study due to its potential for CYP3A4/5 interaction.

6.5 Patient numbering, treatment assignment or randomization

6.5.1 Patient numbering

Each patient is identified in the study by a Patient Number, that is assigned when the patient is first enrolled for screening and is retained as the primary identifier for the patient throughout his/her entire participation in the trial. The Patient Number consists of the Center Number (Center No.) (as assigned by Novartis to the investigative site) with a sequential patient number suffixed to it, so that each patient is numbered uniquely across the entire database. Upon signing the informed consent form, the patient is assigned to the next sequential Patient Number available to the investigator through the interface.

6.5.2 Treatment assignment or randomization

[figure not shown]
The assignment of a patient to a particular cohort will be coordinated by the sponsor. No randomization list will be required for this study.

6.5.3 Treatment blinding

Treatment is not blinded for this study.

6.6 Study drug dispensation

The investigator or responsible site personnel must instruct the patient or caregiver to take the study drugs as per protocol. Study drug(s) will be dispensed to the patient by authorized site

personnel only. All dosages prescribed to the patient and all dose changes during the study must be recorded on the Dosage Administration Record CRF.

LEE011 will be supplied as capsules for oral use of 10, 50, and 200 mg dosage strength. The capsules will be packaged in bottles. LEE011 will also be supplied in Powder in Bottle (PIB) (1200mg in 125mL amber bottle) or in liquid form and will be packaged in bottles.

6.6.1 Study drug packaging and labeling

LEE011 capsules, PIB and liquid form will be packaged in bottles. Medication labels will be in the local language and comply with the legal requirements of each country. They will include storage conditions for the drug but no information about the patient. The study drug will be labeled and packaged under the responsibility of the Novartis drug supply management department. The medication will be supplied as open label supply to the sites in a way which allows the patient to take medication at home.

6.6.2 Study drug compliance and accountability

6.6.2.1 Study drug compliance

Compliance will be assessed by the investigator and/or study personnel at each patient visit and information provided by the patient and/or caregiver will be captured in the Drug Accountability Form. This information must be captured in the source document at each patient visit.

Compliance will be assured by administrations of the study treatment under the supervision of investigator or his/her designee, and will be verified by determinations of LEE011 in plasma.

[figure not shown]
6.6.2.2 Study drug accountability

The investigator or designee must maintain an accurate record of the shipment and dispensing of study treatment in a drug accountability log. Drug accountability will be noted by the field monitor during site visits and at the completion of the study. Patients will be asked to return all unused study treatment and packaging on a regular basis, at the end of the study or at the time of study treatment discontinuation.

At study close-out, and, as appropriate during the course of the study, the investigator will return all used and unused study treatment, packaging, drug labels, and a copy of the completed drug accountability log to the Novartis monitor or to the Novartis address provided in the investigator folder at each site.

6.6.3 Disposal and destruction

The study drug supply can be destroyed at the local Novartis facility, Drug Supply group or third party, as appropriate. Drug supply is to be destroyed at the site only if permitted by local regulations and authorized by Novartis.

7 Visit schedule and assessments

7.1 Study flow and visit schedule

Table 7-1 lists all of the assessments and indicates with an “X”, the visits when they are performed.

For all visits, there is a ± 3 days window on assessments to take into account scheduling over public or religious holidays if not explicitly specified otherwise. All data obtained from these assessments must be supported in the patient’s source documentation. Laboratory assessments that were completed within 72 hours prior to Cycle 1, Day 1 (C1D1) do not need to be repeated.

[figure not shown]

Table 7-1 Visit evaluation schedule

Visit Name	Protocol Section	Screening	Treatment Period													EOT	SEC	
			Cycle 1						Cycle 2			Cycles 3-6			Subsequent cycles			
			1	2	3	4	5	6	7	8	9	10	11	12...	22			23...
Day of Cycle		-21 to -1	1	2	8	15	22	1	15	22	1	15	22	1	22	Last	30 day follow-up	
Obtain Main Informed Consent	7.1.1.	X																
Patient History																		
Demography	7.1.1.3.	X																
Inclusion/exclusion criteria	5.2/5.3.	X																
Medical History	7.1.1.3.	X																
Prior Antineoplastic therapies	7.1.1.3.	X																
Diagnosis and extent of cancer	7.1.1.3.	X																
Prior/concomitant medications	6.4.	Continuous																
Physical examination	7.2.2.1.	X	X		X	X	X	X	X		X	X		X		X		
Performance status	7.2.2.4.	X	X					X			X			X		X		
Height, Weight, BSA	7.2.2.3.	X	X					X			X			X		X		
Vital signs	7.2.2.2.	X	X		X	X	X	X	X		X	X		X		X		
Laboratory assessments	7.2.2.5.																	
Hematology	7.2.2.5.1.	X	X		X	X	X	X	X		X	X		X		X		
Chemistry	7.2.2.5.2.	X	X		X	X	X	X	X		X	X		X		X		
Thyroid	7.2.2.5.3.	X						X			C4,			C8,		X		

Visit Name	Protocol Section	Screening	Treatment Period														EOT	SEC			
			Cycle 1						Cycle 2			Cycles 3-6			Subsequent cycles						
			1	2	3	4	5	6	7	8	9	10	11	12...	22	23...			777	778	
Day of Cycle		-21 to -1	1	2	8	15	22	1	15	22				1	15	22	1	22	Last	30 day follow-up	
														C6			C10,C12, etc.				
Pregnancy test	7.2.2.5.4.	X																		X	
Cardiac																					
ECHO	7.2.2.5.6.	X																		X	
ECG	7.2.2.5.5.	X	X		X	X	X	X	X					X						X	
Efficacy assessments																					
Tumor evaluation	7.2.1.	X ^a								X							C4, C6		C10, C14, C18, etc.	X	
MIBG imaging (neuroblastoma only)	7.2.1.	X ^a								If positive at Screening							If positive at Screening C4, C6		If positive at Screening C10, C14, C18, etc.	X	
BMA and/or Biopsy (neuroblastoma only)	7.2.1.	X ^a								If positive at Screening							If positive at Screening C4, C6		If positive at Screening C10, C14, C18, etc.	X	
CSF Cytology ^b	7.2.1.	X ^a								If positive at Screening only to confirm CR							If positive at Screening C4, C6 to confirm CR		If positive at Screening C10, C14, C18, etc. to confirm CR		
Safety																					
Adverse events	8.1.	Continuous																			
Predictive and Pharmacodynamic	7.2.4.																				

Visit Name	Protocol Section	Screening	Treatment Period														EOT	SEC
			Cycle 1						Cycle 2			Cycles 3-6			Subsequent cycles			
			1	2	3	4	5	6	7	8	9	10	11	12...	22	23...		
Day of Cycle		-21 to -1	1	2	8	15	22	1	15	22	1	15	22	1	22	Last	30 day follow-up	
Biomarkers																		
Collection of archival tumor blocks/slides	7.2.4.1.	X																
BMA and/or Biopsy (neuroblastoma only) ^a	7.2.4.2.	X								If positive at Screening			If positive at Screening C4, C6		If positive at Screening C10, C14, C18, etc.			
LEE011 administration	6.1.2.		Days 1-21					Days 1-21			Days 1-21			Days 1-21				
PK blood sampling ^c	7.2.3.		X	X ^d	X	X	X	X			C3							
CSF for PK ^b	7.2.3.2.		if available when collected for efficacy assessment or routine/ standard clinical purposes															
Antineoplastic therapies since discontinuation of study treatment	7.1.4.															X	X	

^a Screening window = -28 to -1 day(s) prior to first dose of LEE011
^b only for primary CNS (including MRT)
^c An additional PK blood sample will be required if a patient has CSF collected (see Section 7.2.3.2).
^d escalation only, C1D2

7.1.1 Screening

The informed consent form (ICF) must be dated and signed prior to any screening procedures not performed as part of the initial diagnostic work-up of the patient are conducted. Once the ICF is signed, all AEs per the descriptions below will be captured in the Adverse Event CRF.

The screening period starts once a patient has provided written informed consent to participate in the study and ends on the day of first dose of LEE011. Screening assessments have to be done within 21 days prior to the first dose of LEE011 except for baseline tumor imaging scans, CSF cytology, and bone marrow aspirates and/or biopsies which may be done within 28 days prior to the first dose of LEE011 and/or hematologic (ANC, platelet count, and hematocrit) inclusion criteria within 7 days prior to first dose of LEE011.

7.1.1.1 Eligibility screening

The procedures for eligibility check, patient identification number assignments, and coordination among the sites involved will be provided in a separate document prior to study start.

7.1.1.2 Information to be collected on screening failures

Patients who sign an informed consent but fail to be started on treatment for any reason will be considered a screen failure. The reason for not being started on treatment will be entered on the Screening Log eCRF, and each patient's demographic information will be added on the Demography eCRF. No other data will be entered into the clinical database for screen failure patients.

7.1.1.3 Patient demographics and other baseline characteristics

The data that will be collected on patient characteristics at baseline include general demographics, relevant medical history, the diagnosis and extent of their tumor(s) and prior antineoplastic therapies.

[figure not shown]
